Subjects should be seen for all visits/assessments as outlined in the assessment schedule or as close to the designated day/time as possible. Missed or rescheduled visits should not lead to automatic discontinuation. Subjects who prematurely discontinue the study for any reason should be scheduled for a visit as soon as possible, at which time all of the assessments listed for the final End of Treatment (EOT) visit will be performed. At this final visit, all dispensed investigational product should be reconciled, and the adverse event and concomitant medications recorded on the CRF.

Study treatment will begin on Cycle 1 Day 1 (C1D1) with the first administration of the assigned study treatment, depending on the arm into which the subject has been allocated (Part 1) or randomized (Parts 2 and 3). C1D1 should occur on the same day as the allocation/randomization to study treatment, however if this is not logistically possible, it should not be more than 3 days after allocation/randomization in IRT. Each treatment cycle is 21 days for all treatment arms containing NIS793 or 28 days for all other treatment arms. It is recommended that a 28-day gap between Cycle (X) Day 1 and Cycle (X+1) Day 1 is maintained in ruxolitinib + siremadlin combination arm. The duration between cycles should not be shortened to < 28 days due to potential for additive hematotoxicity and adequate time for bone marrow recovery between cycles.

All study visits, assessments and study treatment administration are to be scheduled according to the appropriate number of calendar days from the day of first study treatment administration on C1D1 (whenever possible as per the allowable visit window specified in Table 8-1 below). If one of the investigational drugs is interrupted or permanently discontinued, at any time during the study, all study visits and safety assessments should continue according to the appropriate number of calendar days from C1D1 as per the schedule of assessments, and efficacy assessments must continue as per the scheduled number of weeks from C1D1 as described in

Table 8-2 (Part 1) and Table 8-3 (Parts 2 and 3) for treatment arms with 28-day cycles (all treatment arms not containing NIS793 except the monotherapy arm in Part 3 if ruxolitinib + NIS793 is chosen for Part 3), and Table 8-4 (Part 1) and Table 8-5 (Parts 2 and 3) for treatment arms containing NIS793.

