Safety summaries (tables, figures) include data from the pre-treatment period (to display the baseline status e.g. for ECG) and the on-treatment period, i.e. data from the post-treatment period with the exception of deaths should not be included unless requested from Health Authorities or external committees.

In particular, summary tables for adverse events (AEs) will summarize on-treatment events, with a start date during the on-treatment period, the so-called ***treatment-emergent*** AEs. Additionally, all (study treatment related/ regardless) AEs and SAEs with a start date during the overall safety period will be summarized.

However, all safety data (including those from the post-treatment period) will be listed and those collected during the pre-treatment, post-treatment overall safety period and post-treatment period are to be flagged.

For the final analysis, all extension treatment phase safety data will be listed and those collected during post-treatment overall safety period and post-treatment period are to be flagged. The safety data in part 1 core and extension phase will be summarized in tables for the extension treatment phase clinical trial safety disclosure.

Windows for multiple assessments

In order to summarize data collected over time (including unscheduled visits), the assessments will be time slotted. The following general rule will be applied in creating the assessment windows: If more than one assessment is done within the same time window, the assessment performed closest to the target date will be used. If two assessments within a time window are equidistant from the target date, then the assessment that occurred later will be used. If multiple assessments occur on the same date then the worst case will be used. Data from all assessments (scheduled and unscheduled), including multiple assessments, will be listed.

The following time windows are defined for descriptive summary on spleen imaging, spleen length palpation, ePROs, laboratory assessments [REDACTED] (Tables 2-1, 2-2, and 2-3) by visit regardless of core or extension treatment phases. The end of treatment assessment will be mapped into the time points as needed.

Table 2-1 Time windows for imaging assessments (MRI/CT of abdomen)

Time Point	Planned Visit Timing	Time Window Definition
Screening/Baseline	On or before Study Day 1*	≤ Study Day 1
Cycle 7 Day 1	Study Day 168	Study Days 140 – 196
Cycle 13 Day 1	Study Day 336	Study Days 308 – 364
Every 6 cycles thereafter		

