Cycle $y=13+6*k$ Day 1 (with $k = 1, 2, \dots$)	Study Day $(13+6*k-1)*28$	Study Days $(13+6*k-1)*28-28$ to $(13+6*k-1)*28+28$

* Study Day 1 = Date of first administration of study treatment (start of study treatment)

EOT core and EOT extension assessments are mapped to the corresponding time points based on the defined time window.

Table 2-2 Time windows for ePROs, laboratory assessments (chemistry, coagulation, urinalysis and thyroid function) [REDACTED]

Time Point	Planned Visit Timing	Time Window Definition
Baseline (Cycle 1 Day 1)	On or before Study Day 1*	≤ Study Day 1
Cycle 2 Day 1	Study Day 29	Study Days 15 – 42
Cycle 3 Day 1	Study Day 57	Study Days 43 – 70
Cycle 4 Day 1	Study Day 85	Study Days 71 – 98

Cycle 5 Day 1	Study Day 113	Study Days 99 – 126
Cycle 6 Day 1	Study Day 141	Study Days 127 – 154
Cycle 6+k Day 1 (with k = 1, 2, ...)	Study Day (6+k-1)*28+1	Study Day (6+k-1)*28+1-14 to (6+k-1)*28+14
Post treatment		
30-day safety follow-up	Post treatment study day 30	Post treatment study days 23 – 37
90-day safety follow-up	Post treatment study day 90	Post treatment study days 83 – 97
105-day safety follow-up	Post treatment study day 105	Post treatment study days 98 – 112
150-day safety follow-up	Post treatment study day 150	Post treatment study days 136 – 164

* Study Day 1 = Date of first administration of study treatment (start of study treatment)
 EOT core and EOT extension assessments are mapped to the corresponding time points based on the defined time window.
 Post treatment study day 1 = end of study treatment date + 1
 Post treatment visits are for laboratory chemistry assessments only
 90-day safety follow-up visit for NIS7393 arm(s)
 90-day safety follow-up visit, and 150-day safety follow up visit are for sabatolimab arm(s)
 105-day safety follow-up visit is for crizanlizumab arm(s)

Table 2-3 Time windows for spleen length palpation assessments and hematology laboratory assessments

Time Point	Planned Visit Timing	Time Window Definition
Baseline (Cycle 1 Day 1)	On or before Study Day 1*	≤ Study Day 1
Cycle 1 Day 15	Study Day 15	Study Days 8 – 21
Cycle 2 Day 1	Study Day 29	Study Days 22 – 35
Cycle 2 Day 15	Study Day 43	Study Days 36 – 49
Cycle 3 Day 1	Study Day 57	Study Days 50 – 63
Cycle 3 Day 15	Study Day 71	Study Days 64 – 77
Cycle 4 Day 1	Study Day 85	Study Days 78 – 98
Cycle 5 Day 1	Study Day 113	Study Days 99 – 126
Cycle 6 Day 1	Study Day 141	Study Days 127 – 154

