Ruxolitinib (INC424) Rineterkib (LTT462)	Date of last administration of a non - zero dose of the study drug.	Example 1: A patient had a permanent discontinuation of the study drug on 06Jan2013 after being put on a temporary interruption since 01Jan2013. In this case the last date of exposure is 31Dec2012.
Siremadlin (HDM201) Crizanlizumab (SEG101) Sabatolimab (MBG453) NIS793	The planned end date of the last cycle in which the last non-zero dose of the investigational drug was last administered. Note: If the patient died or was lost to follow-up before the derived last date, the last date of exposure to investigational drug is the date of death or the date of last contact, respectively. If the derived last date of exposure goes beyond the data cut-off date, it should be truncated to the date of data cut-off.	Example 2: Siremadlin is in a 28-day cycle with once a day administration for Day 1-5 of each cycle. The last date of exposure is the date of administration in the last cycle + 23 days. Example 3: Crizanlizumab is in a 28-day cycle with one iv infusion in the beginning of the cycle and with a 2 nd loading dose after 14 days of initial dosing for Cycle1 only. The late dose of exposure is the date of last infusion in Cycle 1 + 13 days if Cycle 1 is the last cycle.

		
The last date of exposure is the date of first infusion in the last cycle + 27 days if the last cycle is post Cycle 1.
 
Example 4: Sabatolimab is in a 28-day cycle with one iv infusion in the beginning of the cycle. The last date of exposure is the date of first infusion in the last cycle + 27 days
 
Example 5: NIS793 is in a 21-day cycle with one iv infusion in the beginning of the cycle. The last date of exposure is the date of first infusion in the last cycle + 20 days

--	--	--

Summary of duration of exposure of an investigational drug will include categorical summaries based on 12 weeks intervals and using descriptive statistics (mean, standard deviation etc). The duration includes the periods of temporary interruption.

Cumulative dose

Cumulative dose of a study treatment is defined as the total dose given during the study treatment exposure and will be summarized for each of the study treatment components. The **actual cumulative dose** refers to the total actual dose administered, over the duration for which the subject is on the study treatment as documented in the Dose Administration eCRF.

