2.7.1 Secondary endpoints

All secondary efficacy endpoints will be analyzed using the Full Analysis Set (FAS).

Proportion of subjects achieving improvement of hemoglobin level (NOT applicable)

Hemoglobin is measured at baseline and at least once per cycle. The change from baseline will be summarized by treatment group using descriptive statistics. Individual hemoglobin level at different time points will be displayed graphically by treatment group.

The proportion of subjects achieving improvement in hemoglobin ≥ 1.5 g/dL and ≥ 2.0 g/dL, respectively, from baseline to the end of Week 24, and the end of Week 48 will be summarized using descriptive statistics (N, %) by treatment arm along with two-sided exact binomial 95% CIs [[Clopper and Pearson 1934](#)]. The proportion will be calculated using FAS subjects as the denominator; the numerator will be based on the number of subjects with a baseline measure and a post-baseline measure of the corresponding time-point.

Change in spleen volume and spleen length

Spleen volume will be measured by MRI/CT at baseline, the end of every 24 weeks (8 cycles for NIS793 arms and 6 cycles for all other arms) and at EOT (if not performed in the past 12 weeks) for Part 1 core treatment phase and extension phase. The change from baseline will be summarized at each scheduled assessment time point by treatment group using descriptive statistics. The change from baseline at the end of Week 24 will be displayed graphically for individual subjects by treatment groups.

The proportion of patients with a spleen volume progression will be summarized using descriptive statistics (N, %) at the end of Week 24 and separately at the end of Week 48 by treatment group.

The proportion of subjects achieving at least 25% and 35% reduction in spleen volume from Baseline to the end of Cycle 8 (NIS793 arms) or Cycle 6 (all other arms) and the end of Cycle 16 (NIS793 arms) or Cycle 12 (all other arms) during the core treatment phase as measured by MRI or by CT will be summarized descriptively.

Spleen length measurement will be conducted by manual palpation. Manual palpation will be performed on days 1 and 15 of cycles 1 to 3, and day 1 of subsequent cycles for Part 1 core treatment phase and extension treatment phase. The change from baseline at each planned

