scheduled point will be summarized by treatment group using descriptive statistics. The change from baseline at the end of Week 24 will be displayed graphically for individual subjects by treatment groups.

The proportion of subjects who achieved at least 50% spleen length reduction from baseline for subjects with baseline splenomegaly that is palpable at greater than 10 cm, or became not palpable for subjects with baseline splenomegaly that is palpable at $\geq 5\text{-}10$ cm will be calculated at the end of Cycle 4 (NIS793 arms) or Cycle 3 (all other arms), and at the end of Cycle 8 (NIS793 arms) or Cycle 6 (all other arms), and at the end of Cycle 16 (NIS793 arms) or Cycle 12 (all other arms).

Change in symptoms assessed by MFSAF and EORTC

Symptoms of myelofibrosis will be measured by MFSAF v4.0 and EORTC QLQ-C30 for the core treatment phase. Due to enrollment halt, EORTC data is not available for Parts 2 and 3 of the study.

MFSAF v4.0

MFSAF v4.0 ([Appendix 5.6](#)) is a harmonized, consensus-based PRO questionnaire recently developed for use in MF trials by a PRO Consortium Working Group ([Gwaltney et al 2017](#)), which focuses on the 7 core symptoms of MF: fatigue, night sweats, pruritus, abdominal discomfort, pain under the ribs on the left side, early satiety and bone pain.

Subjects record symptom severity at its worst for each of the 7 symptoms on an 11-point numeric rating scale, from 0 (absent) to 10 (worst imaginable). The 7-day recall format is used in this study. The Total Symptom Score (TSS) is calculated as the average of the observed individual item responses on the 0 to 10 scale multiplied by 7, resulting in a TSS ranging from 0 to 70. At least four items must be completed to calculate the TSS from the 7-day recall format of the MFSAF v4.0. MFSAF v4.0 is collected at Screening, C1D1, Day 1 of all subsequent cycles of treatment, as well as the EOT visit.

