The change from baseline in MFSAF total symptom score and individual symptoms will be summarized with descriptive statistics by treatment group at each scheduled assessment time point for Part 1. The change from baseline at the end of Week 24 will be displayed graphically for individual subjects by treatment groups. The proportion of subjects with no worsening in symptom at the end of Week 24 and Week 48 will be summarized. The proportion will be calculated using FAS subjects as the denominator; the numerator will be based on the number of subjects with a baseline measure and a post-baseline measure of the corresponding time-point. The symptom worsening is defined as an increase in TSS of 10 or more from baseline.

The proportion of subjects who achieved at least 50% reduction in MFSAF v4.0 Total Symptom Score (TSS) at the end of Cycle 4 (NIS793 arms) or Cycle 3 (all other arms), at the end of Cycle 8 (NIS793 arms) or Cycle 6 (all other arms) and at the end of Cycle 16 (NIS793 arms) or Cycle 12 (all other arms) respectively from baseline will be calculated.

Progression free survival (PFS) (NOT applicable)

PFS is defined as the time from the date of randomization to the date of the first documented progressive splenomegaly, or accelerated phase, or deteriorating cytopenia, or leukemic transformation or death due to any cause. See Protocol Section 8.3.2.4 for the details of the PFS events definition. The PFS event and the corresponding date are taken from the Progressive Disease Assessment CRF page.

PFS will be analyzed using the FAS population according to the randomized treatment group assigned at randomization. The PFS distribution will be estimated using the Kaplan-Meier method, and the Kaplan-Meier curves, medians and 95% confidence intervals of the medians will be presented for each treatment group. The hazard ratio for PFS comparing a combination treatment with ruxolitinib single agent will be calculated, along with its 95% confidence interval, using a Cox model.

PFS will be censored if no PFS event is observed before the cut-off date or the date when a new anti-neoplastic therapy or another investigational treatment is started, whichever occurs earlier. The censoring date will be the date of last adequate assessment before a new anti-neoplastic therapy or another investigational treatment is started, if it occurred, else the date of last adequate assessment before the cut-off date.

Disease Progression

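### The SAP's cycle-labelled visit windows follow a 28-day grid but also cover the 21-day NIS793 arm, so its by-visit summaries carry wrong cycle labels and omit about one scheduled visit in four or five

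*SAP*

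**What the plan says.** Protocol Section 8 sets the cycle lengths: "Each treatment cycle is 21 days for all treatment arms containing NIS793 or 28 days for all other treatment arms". The SAP repeats this in Table 2-5: "NIS793 is in a 21-day cycle with one iv infusion in the beginning of the cycle".

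SAP Section 2.1.1 defines time windows for by-visit summaries of spleen imaging (Table 2-1), ePROs and most laboratory panels (Table 2-2), and spleen palpation and hematology (Table 2-3). On-treatment windows are labelled by cycle and day. In Tables 2-2 and 2-3 the Day 1 targets are Days 29, 57, 85, 113 and 141, and later windows run over "Study Day (6+k-1)*28+1-14 to (6+k-1)*28+14". No arm is excluded and there is no 21-day version. The footnotes to Tables 2-2 and 2-3 confirm that the arm is covered: "90-day safety follow-up visit for NIS7393 arm(s" (NIS7393 is evidently a misprint for NIS793).

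The selection rule is: "If more than one assessment is done within the same time window, the assessment performed closest to the target date will be used". Ties go to the later assessment, and assessments that are not selected appear only in listings.

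SAP Section 2.7.1 sets responder proportions for TSS and spleen length by cycle number. The first landmark is "at the end of Cycle 4 (NIS793 arms) or Cycle 3 (all other arms"); the two later ones are set in the same way, at Cycles 8 and 16 for NIS793. For spleen volume the section describes the schedule as "the end of every 24 weeks (8 cycles for NIS793 arms and 6 cycles for all other arms").

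**The concern.** A grid built on 28-day cycles cannot label 21-day visits correctly. Since 84 = 4 × 21 = 3 × 28, every 84 days bring four NIS793 Day 1 visits but only three windows, so one visit in four must drop out and nearly all the others shift to a wrong label.

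Three things are at stake.

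- **Reporting by cycle.** Protocol Section 12.5.1.3 commits to summarising TSS change by cycle and treatment group, and SAP Section 4 declares no departure from the protocol. Cycle 4 data shown under Cycle 3 do not meet that commitment.
- **Laboratory trends.** Protocol Section 4.5 names renal function as something to monitor in this arm. Protocol Table 8-4 schedules chemistry and urinalysis every cycle, and both use the Table 2-2 windows. A reader following creatinine by cycle would see wrong cycles with some scheduled visits missing.
- **Landmark proportions.** The proportions at the end of Cycle 4, 8 and 16 are never linked to a window. They are right if the programmer maps by study day and wrong if the programmer matches labels.

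**Working it through.** **Inputs.** NIS793 cycle length is 21 days (Protocol Section 8). ePRO and chemistry visits fall on Day 1 of each cycle; palpation and hematology also on Day 15 of Cycles 1 to 3 (Protocol Section 8.3.2.2 and Table 8-4). Windows, targets and selection rule are from SAP Section 2.1.1.

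**Reproducing the SAP's grid.** Target = (c−1)×28+1, window from target−14 to (c−1)×28+14. For c = 3 this gives target 57 and window 43–70; for c = 6, target 141 and window 127–154. Every Table 2-2 row is reproduced. A 28-day schedule run through Tables 2-2 and 2-3 loses no visit and mislabels none.

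**NIS793 nominal days.** Day 1 of cycle c falls on (c−1)×21+1: C2 = 22, C3 = 43, C4 = 64, C5 = 85, C6 = 106, C7 = 127, C8 = 148, C9 = 169. Day 15 visits fall on Days 15, 36 and 57.

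**Table 2-2, up to Day 169**

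| Window label | Target | NIS793 visits inside | Used |
|---|---|---|---|
| C2D1 | 29 | C2D1 (22) | C2D1 |
| C3D1 | 57 | C3D1 (43, 14 days off), C4D1 (64, 7 days off) | C4D1 |
| C4D1 | 85 | C5D1 (85) | C5D1 |
| C5D1 | 113 | C6D1 (106) | C6D1 |
| C6D1 | 141 | C7D1 (127, 14 days off), C8D1 (148, 7 days off) | C8D1 |
| C7D1 | 169 | C9D1 (169) | C9D1 |

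Unused: C3D1 and C7D1, 2 of 8 (25%). Mislabelled: 5 of 6 filled windows.

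**Table 2-3, up to Day 169.** C1D15 and C2D1 are correct. The C2D15 window (36–49, target 43) holds C2D15 (Day 36) and C3D1 (Day 43) and uses C3D1. The C3D1 window takes C3D15 (Day 57). The C3D15 window takes C4D1 (Day 64). From C4D1 on it behaves as Table 2-2. Unused: C2D15 and C7D1, 2 of 11 (18%). Mislabelled: 7 of 9.

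**Up to Day 337.** C11D1 (Day 211) and C15D1 (Day 295) are also displaced, by Days 232 and 316. Unused: 4 of 16 (25%) in Table 2-2 and 4 of 19 (21%) in Table 2-3.

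**Table 2-1.** The scans at about Days 169 and 337 each fall in one window, so none is lost. Their labels read C7D1 and C13D1, where the arm's own visits are C9D1 and C17D1.

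**Timing variation.** Visits up to C8D1 were moved at random by up to 3 days. Table 2-2 still loses 2 of 7 (29%). Table 2-3, nominally 2 of 10 (20%), loses 27% on average, with a range of 20% to 40%.

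**Landmarks.** End of Cycle 4, 8 and 16 falls on 4×21+1 = 85, 8×21+1 = 169 and 16×21+1 = 337. These are exact targets in Tables 2-2 and 2-3, under labels C4D1, C7D1 and C13D1. Matching the labels C5D1, C9D1 and C17D1 instead would give:

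| Label | Window | Visit used | Delay |
|---|---|---|---|
| C5D1 | 99–126 | Day 106 | 106−85 = 21 days (3 weeks) |
| C9D1 | 211–238 | Day 232 | 232−169 = 63 days (9 weeks) |
| C17D1 | 435–462 | Day 442 | 442−337 = 105 days (15 weeks) |

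The C9D1 window would be empty for a subject who stops at the planned 24 weeks.

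**The case against.** The strongest reply is that the windows are calendar windows. They are defined in study days, and SAP Section 2.7.1 equates 24 weeks with 8 NIS793 cycles or 6 cycles elsewhere. SAP Section 2.5.3, written for the Part 2 and 3 endpoint, sends the Week 24 assessment to these same windows. Table 2-1 has no C9D1 or C17D1 row, so matching by label is impossible for imaging. On this reading the landmark visits are captured, one value per window is the declared rule, and nothing is lost from the listings. The arm is also small, has no extension phase, and may have few or no data as late as Day 337.

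Much of this stands. Study day is the better-supported reading, so the delays of 3, 9 and 15 weeks are what a label match would cost and not the expected result. For TSS and spleen length, however, C5D1, C9D1 and C17D1 windows do exist, and the SAP does not rule out their use. Nor does the calendar reading rescue the printed labels: a calendar window should carry a week, and these carry cycles that are wrong for this arm. The nominal Table 2-3 counts are also sensitive to visit timing, because Days 22, 36, 64 and 127 sit on window edges, but the simulated variation never takes the loss below its nominal figure.

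**Conclusion.** The point holds. Applied as written, the rule puts NIS793 values for TSS, chemistry, hematology and spleen length under the wrong cycle and leaves about one scheduled visit in four (Table 2-2) or five (Table 2-3) out of the by-visit summaries. The counts assume visits on nominal days and no unscheduled assessments. Coagulation and thyroid tests have no fixed on-treatment series in this arm, so no scheduled values are lost for them. Table 2-1 has a label fault only, and baseline and post-treatment windows are unaffected.

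The consequence is modest. The affected outputs are descriptive, in a run-in planned for about 6 subjects. The DLT primary endpoint, the worst-grade laboratory tables and the Week 24 and 48 no-worsening summary do not change. It should still be corrected, because the error is certain and the correction is cheap.

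**What to change.** Add one sentence to SAP Section 2.1.1: the end of Cycle 4, 8 and 16 (NIS793) and of Cycle 3, 6 and 12 (other arms) maps to Days 85, 169 and 337 (Weeks 12, 24 and 48). Then choose one of two options.

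1. Label the common windows by week. This corrects the labels and keeps the arms comparable on calendar time, but two NIS793 visits still compete for some windows.
2. Add a window table for NIS793 with Day 1 targets at (c−1)×21+1, plus or minus 10 days for the Table 2-2 assessments. For palpation and hematology, add targets at Days 15, 36 and 57 and cut at the midpoints between targets. This keeps every scheduled visit: with the Table 2-2 version, all 8 Day 1 visits from C2D1 to C9D1 return to their own label.

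The cost is the mapping sentence plus either new labels or one extra table for one small arm. If tables have already been produced, confirm which mapping was used and relabel or footnote the NIS793 columns.
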